4.7.1 Exposure of Study Medication

Exposure to study treatment (total number of injections [lampalizumab or sham] and duration of treatment [through Week 48 or Week 96, as appropriate]) will be summarized by treatment arm. Duration of treatment will be defined based on the difference (in days)

between the dates of the first and last injection (lampalizumab or sham) plus 1 day for the time period summarized.

4.7.2 Adverse Events

Verbatim descriptions of treatment-emergent adverse events will be coded using the latest version of MedDRA. A treatment-emergent adverse event is defined as any new adverse events reported or any worsening of an existing condition on or after the first dose of study treatment. Adverse events with missing onset date will be considered to be treatment emergent. Adverse events with partially missing onset date will also be included as treatment emergent when the month (if it was recorded) and the year occur on or later than the month and year of the initial study treatment date.

Adverse events will be tabulated by body system and preferred term. Separate summaries will be prepared for all non-ocular and all ocular adverse events, with ocular events in the study eye and fellow eye summarized separately as appropriate.

Summaries will be provided for each of the following categories:

- All adverse events
- All adverse events by severity
- Serious adverse events
- Adverse events suspected to be caused by study treatment as assessed by the investigator
- Adverse events leading to discontinuation of study treatment
- Adverse events leading to interruption of study treatment
- Adverse events of special interest as defined in the protocol, specifically:
 - Sight-threatening adverse events (causes a decrease of ≥ 30 letters in visual acuity score lasting more than 1 hour, requires surgical intervention to prevent permanent loss of sight, associated with severe intraocular inflammation, in the opinion of the investigator, it may require medical intervention to prevent permanent loss of sight)
 - Suspected transmission of an infectious agent by the study drug
 - Adverse events resulting from medication error
 - Cases of potential drug-induced liver injury

Ocular adverse events will also be presented on a per-injection basis (i.e., number of events/total number of injections given). Selected adverse events will be reviewed separately (e.g. adverse events that occurred in patients who received treatment with both Lucentis® [ranibizumab injection] and lampalizumab in the study eye or adverse events that are IOP-related).

Patient deaths and primary cause of death will be summarized.

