Only one eye will be chosen as the study eye. If both eyes are eligible to become the study eye, the eye with the worse visual function as determined by the investigator and the patient will be the study eye. If both eyes have the same visual function, the eye with the larger area of GA will be selected as the study eye.

After screening has been completed, eligible patients will be randomized in a 2:1:2:1 ratio so that approximately 312 patients will receive study drug treatment Q4W and 156 patients will receive sham treatment Q4W for a total of 24 treatments; 312 patients will receive study drug treatment Q6W and 156 patients will receive sham treatment Q6W for a total of 16 treatments. The study population will be enriched (ratio of 1.5:1) for the biomarker-positive population relative to the biomarker-negative population (see Section [3.3.2.2](#)).

Randomization will be stratified by biomarker status (positive vs. negative) (as determined by the investigational cobas[®] CFI Profile assay), baseline BCVA ETDRS chart Snellen equivalent (20/50 or better vs. worse than 20/50), sex (women vs. men), and microperimetry eligibility (yes vs. no).

Patients will be treated according to the dosing schedule for the assigned treatment arms as outlined in [Table 2](#) and [Table 3](#).

Table 2 Every 4 Weeks Dosing Treatment Arms

Treatment Arm	Day Visit		Week Visit																									
	1	8 ^a	4	8	12	16	20	24	28	32	36	40	44	48	52	56	60	64	68	72	76	80	84	88	92	96 ^a		
BM+ Lampalizumab (N = 188)	x		x	x	x	x	x	x	x	x	x	x	x	x	x	x	x	x	x	x	x	x	x	x	x	x		
BM+ Sham (N = 94)	x		x	x	x	x	x	x	x	x	x	x	x	x	x	x	x	x	x	x	x	x	x	x	x	x	x	
BM- Lampalizumab (N = 124)	x		x	x	x	x	x	x	x	x	x	x	x	x	x	x	x	x	x	x	x	x	x	x	x	x		
BM- Sham (N = 62)	x		x	x	x	x	x	x	x	x	x	x	x	x	x	x	x	x	x	x	x	x	x	x	x	x		

^a Study treatment is not administered at the Day 8 visit and Week 96 (final visit).

BM+ = CFI profile biomarker-positive; BM – = CFI profile biomarker-negative.

Table 3 Every 6 Weeks Dosing Treatment Arms

Treatment Arm	Day Visit		Week Visit															
	1	8 ^a	6	12	18	24	30	36	42	48	54	60	66	72	78	84	90	96 ^a
BM+ Lampalizumab (N = 188)	x		x	x	x	x	x	x	x	x	x	x	x	x	x	x	x	
BM+ Sham (N = 94)	x		x	x	x	x	x	x	x	x	x	x	x	x	x	x	x	
BM- Lampalizumab (N = 124)	x		x	x	x	x	x	x	x	x	x	x	x	x	x	x	x	
BM- Sham (N = 62)	x		x	x	x	x	x	x	x	x	x	x	x	x	x	x	x	

^a Study treatment is not administered at the Day 8 visit and Week 96 (final visit).

BM+ =CFI profile biomarker-positive; BM- =CFI profile biomarker-negative

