The first study treatment will be administered on the same day as randomization (Day 1 visit). *If a site has an unexpected issue (e.g., the IxRS is not able to assign the study kit), with the Medical Monitor's permission, the patient's first study treatment may be administered within 3 working days of the Day 1 visit. The following assessments will be repeated on the day of the study treatment: slit lamp examination, indirect ophthalmoscopy, and pre- and post-treatment IOP measurement (recorded on Day 1 eCRF and dated accordingly).*

Study treatment visits will be scheduled Q4W (± 5 days) or Q6W (± 5 days) relative to the Day 1 visit date. Randomized patients will have the first intravitreal injection of lampalizumab or sham injection administered by the investigator on Day 1 and will have safety and ocular assessments performed on Day 8 (± 2 days) visit. At the subsequent scheduled visits (Q4W or Q6W), patients will have safety evaluations performed by the investigator prior to receiving study drug or sham injection. They will be contacted by site personnel 4 (± 2) days after each injection to elicit reports of decrease in vision, eye pain, unusual redness, or any other new ocular symptoms in the study eye. If warranted, patients will be asked to return to the clinic as soon as possible for an unscheduled safety assessment visit (see [Appendix 2](#)). Patient self-administered antimicrobials pre- and post-injection may be used at the investigator's discretion. Patients will be instructed to contact the investigator at any time if they have any health-related concerns.

All assessments for a scheduled visit are to be performed on the same day, except those performed during the screening period.

Study treatment should not occur earlier than 22 days after the previous treatment. Missed study treatments will not be made up.

After the Day 1 visit, if a patient misses a study visit when ocular images are scheduled to be taken (see [Appendix 1](#)), the images must be obtained at the next scheduled visit.

Patients are not expected to attend their scheduled visits if there are extenuating circumstances justifying their inability to come to the clinic.

For masking requirements, see [Section 4.2.2](#).

Patients who are prematurely discontinued from study treatment will be encouraged to undergo as many scheduled visits as possible with emphasis on completing Week 48 and Week 96 visits.

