4.6.2 Study Treatment Discontinuation

The investigator has the right to discontinue a patient from the study treatment for any medical condition that the investigator determines may jeopardize the patient's safety if he or she continues in the study treatment, for reasons of non-compliance (e.g., missed doses, visits), if the patient becomes pregnant, or if the investigator determines it is in the best interest of the patient. The reason for the treatment discontinuation should be recorded on the appropriate eCRF.

Treatment discontinued patients will not be replaced or allowed to re-start the study treatment. However, they should be strongly encouraged to stay in the study and undergo as many scheduled visits as possible with emphasis on the Weeks 48 and 96 visits.

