5.3.1 Adverse Event Reporting Period

Investigators will seek information on AEs at each patient contact. All AEs, whether reported by the patient or noted by study personnel, will be recorded in the patient’s medical record and on the Adverse Event eCRF.

After informed consent has been obtained **but prior to initiation of study drug**, only SAEs caused by a protocol-mandated intervention (e.g., invasive procedures such as biopsies, discontinuation of medications) should be reported (see Section 5.4.2 for instructions for reporting SAEs).

After initiation of study drug, all AEs will be reported until the last study visit. After this period, the investigator should report any serious adverse events that are believed to be related to study treatment. (see Section 5.6).

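### The per-injection ocular adverse event rate has no post-injection window, so events that accrue with calendar time look up to 1.5 times as frequent in Q6W as in Q4W

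*SAP*

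**What the plan says.** SAP 4.7.2 adds one display to the usual adverse event tables: "Ocular adverse events will also be presented on a per-injection basis (i.e., number of events/total number of injections given"). The sentence does not say which eye is meant or how soon after an injection an event must start.

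The numerator has a start but no end. The same section defines a treatment-emergent event as "any new adverse events reported or any worsening of an existing condition on or after the first dose of study treatment". Protocol 5.3.1 sets the collection period: "After initiation of study drug, all AEs will be reported until the last study visit". Patients who stop treatment remain under observation where possible; Protocol 4.6.2 says "they should be strongly encouraged to stay in the study and undergo as many scheduled visits as possible". Protocol 3.1 says of missed doses: "Missed study treatments will not be made up".

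The denominator follows the schedule. Protocol 3.1 plans 24 treatments in the Q4W arms. For Q6W it says "312 patients will receive study drug treatment Q6W and 156 patients will receive sham treatment Q6W for a total of 16 treatments". SAP 2 places the final visit at Week 96 for every arm.

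**The concern.** A per-injection rate is informative when injections cause the events. Here the numerator also takes in events that arise simply because time passes, such as cataract progression or the appearance of new vessels. Both schedules have the same calendar time to collect such events, but Q6W divides them by fewer injections. Protocol 3.3.1 presents Q6W as the lower-burden alternative to Q4W, so readers will set the two regimens side by side. A per-injection table that shows Q6W as worse when nothing differs would mislead that comparison.

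A second effect comes from treatment stopping. A patient who stops or misses injections but keeps attending can add events without adding to the denominator. SAP 4.7 specifies no person-time rate that would expose either effect. The duration of treatment in SAP 4.7.1 runs only from first to last injection, so it does not measure follow-up after stopping.

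**Working it through.** **Planned injections (Protocol 3.1, SAP 2).** Q4W is dosed from Day 1 to Week 92: 92/4 + 1 = 24. Q6W is dosed from Day 1 to Week 90: 90/6 + 1 = 16. Both match the stated totals.

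**Week 96, background events only.** With rate λ and follow-up T the same in both arms, the per-injection rate is λT/24 for Q4W and λT/16 for Q6W. The ratio is 24/16 = 1.50 whatever λ is. As an illustration, assume one background event per patient-year and 312 patients per lampalizumab arm. About 574 events occur in each arm, over 312 × 24 = 7,488 and 312 × 16 = 4,992 injections. The rates are 0.077 and 0.115 per injection. Assumed rates of 0.5 or 2 per year give the same ratio.

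**Week 48.** SAP 2.5 cuts non-imaging data at Study Day 350 (Q4W) and 357 (Q6W), so the Week 48 injection at Day 337 is included. Injections number 13 and 9.
- Equal follow-up: 13/9 = 1.44.
- Allowing for the cutoffs: (13/9) × (357/350) = 1.47.

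**Mixed causes.** Let f be the share of Q4W events caused by injection. That part has the same per-injection rate in both arms, and the rest is multiplied by 1.5. The ratio is f + 1.5(1 − f).

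| f | Q6W:Q4W at Week 96 |
|---|---|
| 0 | 1.50 |
| 0.25 | 1.375 |
| 0.50 | 1.25 |
| 0.75 | 1.125 |
| 1 | 1.00 |

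**Stopping treatment.** Assume a share d stops at a time uniform over 96 weeks. Those who stop receive on average 12.5 (Q4W) or 8.5 (Q6W) injections.
- If they stay in follow-up, the Q4W rate is multiplied by 24/[24(1 − d) + 12.5d]. At d = 10% this is 24/22.85 = 1.05, and for Q6W 16/15.25 = 1.05. At d = 25% the factors are 1.14 and 1.13.
- If they leave the study when they stop, follow-up shrinks too. At d = 10% mean follow-up is 0.9 × 96 + 0.1 × 48 = 91.2 weeks. The Q4W factor is (91.2/22.85)/(96/24) = 0.998, and the Q6W factor is 0.997. There is no rise.

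**After the change.** With one window of w days, shorter than the dosing interval, the background contribution is λw per injection in both arms and the ratio is 1.00. Events per patient-year also give 1.00, and that ratio does not move when patients stop treatment but stay.

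**The case against.** The rate is supplementary and descriptive. No test or decision rule uses it, and the SAP states no purpose for it. SAP 4.7.2 also tabulates ocular events by preferred term, severity, seriousness, suspected causality and special interest. With the same planned follow-up in every arm, those per-patient tables are not affected by 24 versus 16. This stands, and it limits how much the flaw matters.

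For events that injections do cause, a per-injection denominator is the right one. Protocol 5.1 lists events thought to be linked to the route of administration or the drug's pharmacology, including conjunctival hemorrhage, endophthalmitis and transient pressure rise. This also stands, so 1.5 is the upper end at Week 96.

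A reader might infer three stronger claims that the documents do not support.
- **Lampalizumab versus sham is distorted by the schedule.** Pooling sham (20 injections on average) would give 20/24 = 0.83 for Q4W and 20/16 = 1.25 for Q6W under equal background rates. But SAP 4.1.2 classifies sham safety patients by assigned frequency. The pooling statement in SAP 2.3.1 concerns sample size, and the pooled model in SAP 4.5 concerns efficacy. SAP 4.7 leaves the display open.
- **Any arm with more discontinuation shows a higher rate.** This holds only for patients who stop or miss treatment and stay. The documents give dropout assumptions (15% by one year, 25% by two years for microperimetry) but no rate for stopping and staying.
- **Fellow-eye events are mixed in.** Protocol 6.5.1 separates the eyes, and SAP 4.7.2 does so as appropriate. The per-injection sentence merely fails to repeat it.

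Finally, the counting of events after the last injection is inferred from the open-ended definition and the collection period. The per-injection sentence does not say so, but nothing in the plan excludes them.

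**Conclusion.** The point holds as a defect in a descriptive safety display. For ocular events that accrue with calendar time, the stated formula makes Q6W look up to 1.5 times Q4W at Week 96 and about 1.44 to 1.47 times at Week 48. These figures follow from the documents' own schedule and cutoffs, and assume equal background rates and full dosing. The actual ratio depends on the injection-caused share f, which the documents do not give, and can lie anywhere from 1.0 to 1.5 at Week 96.

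The stopping effect is smaller: about 5% if 10% of an arm stop at a uniform time and stay, an assumed figure. It biases a same-frequency comparison only if that share differs between lampalizumab and sham. For example, 10% against 5% (factors 1.050 and 1.025 in Q4W) would give 1.050/1.025, about 2%.

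No efficacy conclusion, alpha level or sample size is touched. The change is worth making because the two regimens will be compared and the plan offers no person-time rate.

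**What to change.** Amend the sentence in SAP 4.7.2 as follows.

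1. **Numerator.** Count study-eye events with onset within one common window after an injection, the same in every arm and shorter than the 22-day minimum between treatments in Protocol 3.1 and 4.3.2.1 (for example 21 days). Count each event once. A 28-day window would not do: Q4W windows could overlap when treatments are 22 days apart, while Q6W windows on schedule would not.
2. **Denominator.** Use injections whose window is complete at the data cutoff, and count only events in those windows. At Week 48 an on-schedule injection on Day 337 has only 13 days (Q4W) or 20 days (Q6W) before the cutoff. With a 21-day window it drops out of both arms, leaving 12 and 8 planned injections.
3. **Comparator.** Show each lampalizumab arm beside sham of the same frequency, using the groups already defined in SAP 4.1.2.
4. **Companion rate.** Present all ocular events, by eye, per patient-year of follow-up, with time counted to the last visit or data cutoff and not to the last injection.

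The cost is SAP wording and derived variables from event, injection and visit dates already collected. The downside is that later injection-related events leave the per-injection rate, but they remain in the per-patient and per-patient-year tables.

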4.7.3 Laboratory Data

A descriptive summary of laboratory values for alternative complement pathway activity (AH50), including changes from baseline and values outside the normal limits, will be generated.

General chemistry, hematology, and urinalysis laboratory results were collected as part of screening eligibility and subsequently only for patients who discontinued study treatment early. Therefore, laboratory results are reviewed by the Sponsor on an individual patient basis. Aggregate summaries will not be provided. Clinically significant laboratory abnormalities will be reported as adverse events and evaluated as part of the adverse event assessments.

4.7.4 Immunogenicity

The number and percentage of patients with positive serum anti-drug antibodies at baseline and post-baseline during the study period will be tabulated. Adverse events occurring in patients with positive serum anti-drug antibodies will be reviewed.

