2.2 SAFETY OBJECTIVES

The safety objectives for this study are as follows:

- To evaluate the local and systemic safety and tolerability of intravitreal injections of 10-mg lampalizumab administered Q4W or Q6W relative to sham control
- To evaluate the clinical significance of anti-therapeutic antibodies directed against lampalizumab

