3.4.2 Safety Outcome Measures

The safety outcome measures for this study are as follows:

- The incidence and severity of ocular adverse events
- The incidence and severity of systemic (non-ocular) adverse events
- Changes and abnormalities in ECG parameters
- The incidence of anti-lampalizumab antibodies

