6.5.3 Anti-Therapeutic Antibodies

Data on ATAs directed against lampalizumab will be summarized by the number and percentage of patients with confirmed positive ATAs.

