2.1.6 Safety Endpoints

The safety outcome measures are as follows:

- The incidence and severity of ocular adverse events
- The incidence and severity of non-ocular adverse events
- Changes and abnormalities in electrocardiogram (ECG) parameters
 - Assessed through Week 24 for patients at selected sites who have undergone ECG evaluation (approximately 100 patients in total)
- The incidence of anti-drug antibodies

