4.2 DEFINITION OF BASELINE

Baseline will be defined as the last available pre-treatment value taken on or before the day of randomization, and will be used for summary of demographic characteristics, as well as for all change-from-baseline analyses of efficacy and safety endpoints.

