4.7 SAFETY ANALYSES

The safety profile of lampalizumab will be assessed through the summary of adverse events, deaths, laboratory results for alternative complement pathway activity, serial ECG results, incidence of anti-drug antibodies, and ocular assessments (e.g., intraocular pressure [IOP]).

At the time of the Week 48 primary efficacy analysis, safety summaries will be produced based on the complete Week 48 data. In addition, summaries for ongoing second year safety data (after Week 48 and up to a single specified clinical cutoff date) will also be produced. At the time of the final analysis, safety summaries will be produced based on cumulative Week 96 data.

Safety outcomes will be summarized based on the safety-evaluable population or ECG-analysis population as appropriate, with patients grouped according to the treatment actually received (see Sections 4.1.2 and 4.1.4).

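### The protocol asks whether anti-lampalizumab antibodies matter clinically, but the SAP plans only a review of adverse events in antibody-positive patients, with no antibody-negative comparison and no rule for baseline positives

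*SAP*

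**What the plan says.** Protocol 2.2 states the objective: "To evaluate the clinical significance of anti-therapeutic antibodies directed against lampalizumab". The matching outcome measure is an incidence, both in Protocol 3.4.2 ("The incidence of anti-lampalizumab antibodies") and in SAP 2.1.6 ("The incidence of anti-drug antibodies").

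The analyses are brief. Protocol 6.5.3 says the antibody data will be "summarized by the number and percentage of patients with confirmed positive ATAs". SAP 4.7.4 has two sentences. The first is "The number and percentage of patients with positive serum anti-drug antibodies at baseline and post-baseline during the study period will be tabulated". The second is "Adverse events occurring in patients with positive serum anti-drug antibodies will be reviewed".

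Three other places bear on how this would be done:

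- SAP 4.7, on grouping: "Safety outcomes will be summarized based on the safety-evaluable population or ECG-analysis population as appropriate, with patients grouped according to the treatment actually received". An antibody table by arm, including sham, can therefore be expected, although 4.7.4 does not repeat this.
- SAP 4.2, on baseline: "Baseline will be defined as the last available pre-treatment value taken on or before the day of randomization".
- Protocol Appendix 1 schedules serum antibody and serum PK samples together on Day 1 and at Weeks 24, 48, 72 and 96.

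**The concern.** The stated analysis does not answer the stated question. Clinical significance is about whether patients who develop antibodies fare differently from patients on the same drug who do not. Reading through the events of the positive patients gives a numerator only. Intraocular inflammation is the obvious example: Protocol 5.1 lists it as a potential safety issue and a focus of the data monitoring committee. A few inflamed eyes among antibody-positive patients could be an antibody effect or simply the rate on drug, and the review as described has nothing to set them against.

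The incidence measure has a smaller gap. SAP 4.7.4 defines no treatment-emergent antibody category, gives no denominator, and has no rule for patients already positive on Day 1. SAP 4.7.2 does define treatment emergence for adverse events, down to missing onset dates.

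At stake is a safety objective reported without a controlled analysis, with definitions chosen after unmasking. The primary endpoint is not affected.

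**Working it through.** The documents state no antibody rate, sample size or precision for this point, so there is no figure to reproduce. The check sets the text side by side and then sizes the two gaps under labelled assumptions.

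**1. Is there an analysis by antibody status anywhere?**

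| Place | What it plans | By antibody status? |
|---|---|---|
| Protocol 6.5.3 | count and percentage positive | no outcome linked |
| SAP 4.7.4 | percentage positive; review of events in positives | positives only |
| SAP 4.7.2 | adverse events by category; study eye and fellow eye separate as appropriate | no |
| SAP 4.7.5 | intraocular inflammation by grade | no |
| SAP 4.6 | optional PK and exposure-response work | antibodies not mentioned |

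Neither document specifies a comparison of safety, GA area or drug concentration between antibody-positive and antibody-negative patients.

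**2. What a review of positives alone can show.**

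Input from SAP 2.3.2: 312 patients per lampalizumab arm, so 2 × 312 = 624. Assumptions: 10% or 5% positive (62 or 31 patients), and a 3% event rate regardless of antibody status.

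- Expected cases among positives: 62 × 0.03 = 1.9; 31 × 0.03 = 0.9.
- P(2 or more of 62) = 1 − 0.97^62 − 62 × 0.03 × 0.97^61 = 1 − 0.151 − 0.290 = 0.56.
- P(2 or more of 31) = 1 − 0.97^31 − 31 × 0.03 × 0.97^30 = 1 − 0.389 − 0.373 = 0.24.
- Larger counts are informative. Among 62, P(5 or more) is 0.04 and P(6 or more) is 0.01 (binomial tails).

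Each of these uses the 3%, the rate in comparable patients without antibodies. SAP 4.7.4 does not ask for that figure.

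**3. How sharp would a comparison be?**

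Under the same assumptions, 2 of 62 is 3.2% with an exact (Clopper-Pearson) 95% interval of 0.4% to 11.2%. For 17 of 562 it is 3.0%, interval 1.8% to 4.8%. As a gauge only, since no test is proposed, exact Fisher power at two-sided 0.05 for 62 versus 562 patients is 93% for 15% versus 3%, 57% for 9% versus 3%, and 24% for 6% versus 3%. For 31 versus 593 it is 73%, 35% and 15%. Large differences would be visible and a doubling would not.

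**4. Incidence.**

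Let b be the proportion positive at baseline and c the conversion proportion among baseline negatives. If baseline positives are included in the post-baseline figure and all stay positive:

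- post-baseline percentage positive = b + (1 − b)c
- excess over c = b(1 − c)

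With c = 5% and 312 patients per arm (b and c are assumed):

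| b | Post-baseline positive | Converters / baseline negatives | Excess (points) |
|---|---|---|---|
| 0% | 5.0% (15.6) | 15.6 / 312 | 0 |
| 2% | 6.9% (21.5) | 15.3 / 305.8 | 1.9 |
| 5% | 9.75% (30.4) | 14.8 / 296.4 | 4.75 |
| 10% | 14.5% (45.2) | 14.0 / 280.8 | 9.5 |
| 15% | 19.25% (60.1) | 13.3 / 265.2 | 14.25 |

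Over b from 0 to 15% and c from 2% to 10%, the excess runs from 0 to 0.15 × 0.98 = 14.7 points.

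A reader given only the two percentages, for the same patients, can bound the converters. The lower bound assumes every baseline positive stays positive, and the upper bound assumes none does. At b = c = 5% that is 312 × (0.0975 − 0.05) = 14.8 up to 312 × 0.0975 = 30.4.

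**The case against.** The strongest reply is that the comparator is not truly absent. SAP 4.7.2 tabulates all events and SAP 4.7.5 tabulates inflammation by grade. The antibody-negative count for any event is then the arm total less the cases found in the review, and its denominator follows from the antibody counts. This stands in part: the data would allow the split. But the plan does not specify it, and a review is not said to yield counts by event.

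Second, a reader might infer that the SAP counts baseline positives in the post-baseline rate and so overstates incidence. The text does not say so. It is silent on the rule and tabulates baseline positivity separately, which would expose a pre-existing rate. A doubling is one assumed scenario.

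Third, concentration and GA area by antibody status may be covered elsewhere. SAP 4.6 refers to a separate modelling and simulation plan that is not available here. The gap can be asserted only for the protocol and SAP.

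Fourth, a comparison by antibody status has its own bias. Status arises after randomization, and patients followed longer give more samples and have more time for events. Some events will precede the first positive sample. With samples at Weeks 24, 48, 72 and 96, the date of conversion is also known only coarsely. This stands in full and limits what the added tables may claim.

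**Conclusion.** The concern holds in a limited form. Protocol 2.2 sets an objective about clinical significance, and the two documents answer it only with an uncontrolled review of events in antibody-positive patients. Under the assumed rates, two or more background cases among 62 positives would appear 56% of the time with no antibody effect, so a short case list settles little without the antibody-negative rate. It would be too strong to say that no case count could be informative: six cases against a known 3% would be.

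On incidence, the fault is an undefined rule. It would also be too strong to say that incidence cannot be read at all. Two percentages bound it, and a by-arm table adds the sham background. The excess is anywhere from 0 to about 15 points over the assumed ranges, and zero if no patient is positive at baseline.

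Every antibody and event rate above is an assumption; only the 312 per arm comes from the documents. This is a low-cost improvement to a descriptive safety section, with no bearing on alpha or the primary analysis.

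**What to change.** In SAP 4.7.4, before unmasking:

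1. Tabulate by arm, including pooled sham: (a) patients positive at baseline, and (b) patients negative at baseline with at least one positive post-baseline sample, over baseline-negative patients who have a post-baseline sample. Show patients with a missing baseline sample separately, since counting them as converters could bring in pre-existing positives. No titre rule is proposed, because neither document mentions titre.
2. For the lampalizumab arms, add tables by antibody status of study-eye intraocular inflammation and other ocular adverse events, serum concentration by visit, and change in GA area at Weeks 48 and 96. Give 95% confidence intervals and no hypothesis test.
3. For each event in an antibody-positive patient, show whether it began before or after the first positive sample.
4. State that the comparison is descriptive and not causal, because antibody status is post-randomization and depends on length of follow-up.

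The cost is a few sentences and a few tables from samples already scheduled. Protocol 4.2.2 says sham PK samples are generally not assayed, but concentration is requested only for the lampalizumab arms. The sham antibody rows assume that sham antibody samples are assayed; Protocol 5.1 has them drawn from all patients, and neither document exempts them from assay. The downside is wide intervals if few patients are positive.
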